#### Primary outcome:

**Specific aim 1:** The objective of this investigation is to identify the clinical effectiveness of sub-dissociative dose IV Ketamine as an adjunctive treatment for the acutely suicidal patient in the ED.

**Hypothesis 1:** There will be a clinically significant decrease in suicidal ideation (SI) in those treated with Ketamine after 24 hours.

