Suicidal patients, subjectively identified by clinician, upon admission to the ED will be medically cleared by the EM physician, and then meet with the mental health liaison to be screened for admission to the psychiatric department, per normal standard of care. Study investigators will not be available around the clock, but when available will begin the pre-screening method for this investigation. The treating physician will pre-screen them for inclusion and exclusion criteria per an IRB approved check list (Appendix D: Criteria Checklist).

The patient will be approached for informed consent in accordance to with 21 CFR 50. They will be provided with a written document that embodies the elements of the informed consent. The consent will be presented orally to the subject with a witness. Once presented the subject will be given a reasonable time to review the contents and inquire information. Upon signing of the form, a copy shall be given to them.

Once consent is obtained, they will be presented with a paper form to complete the BSSI and MADRS-S. These measures will serve as baseline severity of suicidal wishes and plans, and degree of depression symptoms. Questionnaires will be stored in locked drawer's in the locked office the Division Officers in the Emergency Department, the Inpatient Mental Health ward, or the study coordinator.

Once the patient is deemed medically cleared by the treating physician, the study treatment will be ordered by an ED provider, per the randomization schedule, and administered by an ED nurse (Please see below for more detailed methodology). Those in the experimental arm will be treated with 0.5 mg/kg IV infusion of ketamine over 40 minutes. Those in the control arm will be treated with 100 cc Saline infusion over 40 minutes. (Table 1) Since there are no pharmaceutical treatment specific for acute suicide, it is in accordance to the Declaration of Helsinki (DOH) to utilize a saline placebo control. Vitals will be checked every 5 minutes during infusion. Questionnaires will be repeated at four time points for both arms, once in the ED before drug administration, one at 4 (+/-1) hours post-infusion, whether in the ED or the psychiatric unit, another 24-36 hours after the infusion in the inpatient psychiatric unit, and lastly one-week (+1 day) post treatment by phone call.

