To attain a psychometric baseline, the patient will complete the BSSI and MADRS, on paper forms. After completion of baseline, the clinician will administer a single dose of IV ketamine, per experimental protocol procedure. The specific dose and route of administration were selected based on average dosage and administration from meta-analysis studies. A bolus of ketamine was another common route of administration. However, there is no statistical significance between this and the one selected. This study will not require any wash out periods or concomitant dosing regimens. This dosage and infusion regimen is not considered sedation.

During ketamine infusion, vitals will be checked q5min with serial pulse and blood pressure measurements, and patient will have continuous pulse oximetry (Pox), with all vitals connected to monitors at the nurse's and doctor's stations. In addition, an attendant will be present at all times as per suicidal patient protocol. Treatment will be stopped if pulse or systolic blood pressure increases > 25% of baseline, respiratory rate is sustained at < 7, Pox decreases below 92%, or if severe psychomimetic effects or agitation present.

If treatment is stopped before completion for any reason, the patient will be dropped from the study, and their symptoms will be treated as per usual protocol of the physician. For instance, for severe psychomimetic effects and agitation, benzodiazepines such as midazolam could be considered. If a negative side effect occurs and treatment is stopped, it will be reported to the research monitor immediately.

Post assessment psychometric testing will be repeated at three time points for both arms. The first time point will be 4 hours post treatment, which is the standard time to evaluate acute response to ketamine. This may be collected in the ED or in the Psychiatric Unit. Subsequent questionnaires will be completed either in the ED or in the Psychiatric Unit. ED nurses giving report to the Psychiatric Unit will indicate that the patient is enrolled in the study, and give the time of administration of the study intervention and will indicate when the next questionnaire should be completed. Based on the literature, 24 hours post treatment, our second time point is when half of patients treated with a single dose of IV ketamine have shown reduction in SI.

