## Experimental Procedure

1. Baseline evaluation of suicidal severity (BSSI) & degree of depressive symptoms (MADRS-S) will be evaluated through self-administered questionnaires.
2. The experimental and placebo arms will receive a single dose of IV ketamine, 0.5 mg/kg in 100 cc NS or 100 cc of NS infused over 40 minutes.
3. Post ketamine re-evaluation of outcome measures at four and twenty-four hours will determine clinical effectiveness of ketamine intervention
4. Inspection of admission and transfer time provides time measurement for LOS. This secondary measure is needed to determine efficiency of intervention.
5. Post ketamine re-evaluation of outcome measure at one-week post infusion will elucidate ketamine's durability of effect.

**Table 2:** Description of activities at time points during the study

|  | Study Visit 1
Baseline ( $t_0$ ) | Study Visit 1
4 hours ( $t_1$ ) | Study Visit 1
24 hours ( $t_2$ ) | Study Visit 2
1 week ( $t_3$ ) |
|--|-------------------------------------|------------------------------------|-------------------------------------|-----------------------------------|
|  |                                     |                                    |                                     |                                   |

|  |   |   |   |   |
|--|---|---|---|---|
| Eligibility review and confirmation                    | X |   |   |   |
| Education regarding research & Informed Consent signed | X |   |   |   |
| History & Physical                                     | X |   |   |   |
| Randomization  | X |   |   |   |
| Dispense study drug                                    | X |   |   |   |
| IV Ketamine  | X |   |   |   |
| Vital Signs & ADR* monitored                           | X | X | X |   |
| Review adverse events                                  | X | X | X |   |
| Psychometric testing                                   | X | X | X | X |

\*ADR: Adverse drug reaction

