### 11.6 Data Analysis Plan: Complete description: Background, Objectives, Design, Step by Step how the project is going to be done, Data analysis plan:

**Table 6:** Test Plan of Data Analysis

| Question to be answered   | Type of Analysis                                   | Independent (x)  | Dependent (y)      | Relationship     |
|---|--|--|--------------------|------------------|
| Is there a difference effect of ketamine in those who are high suicide vs. high depressed?                  | McNemar test                                       | High Suicide   | High depressed     | Within           |
| Is there a difference in the placebo between the same two groups?   | McNemar test                                       | High Suicide group                                     | High Suicide group | Within           |
| Is there any difference between ketamine vs. placebo on BSSI & MADRS?                                       | One-way MANOVA                                     | Group  | BSSI; MADRS        | Between          |
| Is there a difference in SI between Ketamine vs placebo   | 2 Independent sample t test                        | Group  | BSSI @ T4          | Between          |
| Is there a difference in depression between Ketamine vs placebo   | 2 independent sample t test                        | Group  | MADRS @ T4         | Between          |
| Is there a difference in effect from placebo when accounting for covariates?                                | MANCOVA  | Fixed factor: Group
Covariates: Demographics        | BSSI, MADRS @ T4   | Between          |
| Is there a difference in effect from ketamine @ the different time points?                                  | Mixed model
Or
Repeated measure ANOVA | Fixed factor: Group                                    | BSSI               | Within & between |
| Is there a difference in group at the different time points, when MADRS is a covariate?                     | Mixed model                                 | Fixed factor: Group
Covariates: MADRS               | BSSI               | Within & between |
| Is there a difference in group at the different time points, when MADRS, and demographics are considered? * | Mixed model                                 | Fixed factor: Group
Covariates: MADRS, demographics | BSSI               | Within & between |

\*This case requires a larger sample size.

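### The 24 h primary hypothesis is not mapped to any test: Table 6's only dated between-arm SI rows say T4, a label absent from the visit schedule, and no row is named primary

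*Combined protocol and SAP*

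**What the plan says.** - **Primary hypothesis (section 9.3).** "There will be a clinically significant decrease in suicidal ideation (SI) in those treated with Ketamine after 24 hours". The one-week question is Hypothesis 2, under the secondary outcomes. Section 9.2 makes the BSSI the primary outcome scale.
- **Schedule (section 10.1, Table 2).** Baseline is t0, 4 hours t1, 24 hours t2 and one week t3. Methods and Materials agrees on the numbering: "24 hours post treatment, our second time point".
- **Questionnaires (section 10.1, General Approach).** "Questionnaires will be repeated at four time points for both arms", counting baseline. The third is "another 24-36 hours after the infusion in the inpatient psychiatric unit"; the fourth is at one week.
- **Experimental Procedure, step 3 (section 10.1).** "Post ketamine re-evaluation of outcome measures at four and twenty-four hours will determine clinical effectiveness of ketamine intervention".
- **Table 6 (section 11.6).** Nine rows, none called primary. Three carry a time: the BSSI t-test, the MADRS t-test and the MANCOVA, all at T4. The row "Is there a difference in SI between Ketamine vs placebo" is the BSSI t-test. The MANOVA row has no time. The first repeated-measures row asks "Is there a difference in effect from ketamine @ the different time points" and offers a mixed model or a repeated-measures ANOVA. The next two rows offer a mixed model only. The last row alone has a footnote: "This case requires a larger sample size".
- **Section 11.5.** The planned minimum is 62 subjects. The linear model for repeat measures is reserved for a sample of 74.

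**The concern.** A reader who goes from Hypothesis 1 to Table 6 to find the test that decides the trial does not find it. The rows that compare SI between arms at a stated time use a label that the schedule does not contain, and the rows that contain the 24 h data do not isolate 24 h.

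Two further passages leave the mapping loose. Hypothesis 1 is worded as a fall in the ketamine arm, although sections 9.2 and 9.3 plainly intend a comparison with saline; section 10.1 itself lists the placebo effect as a limitation, so a fall within one arm could not be credited to ketamine. Step 3 of the Experimental Procedure names 4 h and 24 h together without ranking them.

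At stake is whether the analyst, following Table 6 literally, would run a test that answers the primary hypothesis.

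**Working it through.** **1. Can T4 be 24 h under any numbering in the text?**

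| Source | 4 h | 24 h | 1 week |
|---|---|---|---|
| Table 2 label | t1 | t2 | t3 |
| Order of post-infusion assessments | first | second | third |
| Order of all questionnaires | second | third | fourth |
| T as hours | 4 | 24 | – |

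A 4 appears only for the 4-hour visit (as hours) and for one week (as the fourth questionnaire). No visible numbering gives 24 h the number 4.

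**2. Do the undated rows supply the 24 h test?** The MANOVA gives no time. The repeated-measures rows use all times, and a group effect or group-by-time effect across several visits is not a between-arm test at 24 h unless that contrast is written down. It is not.

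**3. When is the mixed model available?** Section 11.5 opens by requiring 74 subjects for the linear model of repeat measures, against a planned 62. The Table 6 footnote asks for a larger sample in the last row only. The first repeated-measures row can fall back on ANOVA. The row with MADRS as the only covariate has neither a footnote nor an ANOVA alternative, so at 62 the two places disagree about it.

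**4. Plan's own sample-size figure.** Two-sample t-test, alpha 0.05, power 0.80, d = 0.8. Sidedness is not stated; two-sided gives 25.52 per arm, matching the 25.5 in Table 4. The large-correlation entry (r = 0.5 assumed) gives 28.25 against the stated 28.2. Then 2 × 28 = 56 and 56 × 1.10 = 61.6, rounded to 62. The figure reproduces, but section 11.5 ties it to no visit, so it cannot settle what T4 means.

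**5. Power if the t-test is placed at t2.** Noncentrality = d × √(n/2), with df = 2n − 2, two-sided 0.05, d = 0.8:

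| n per arm | Origin | Noncentrality | Power |
|---|---|---|---|
| 26 | 25.5 rounded up | 0.8 × √13 = 2.88 | 0.807 |
| 28 | 31 × 0.9 = 27.9 | 0.8 × √14 = 2.99 | 0.836 |
| 31 | no dropout | 0.8 × √15.5 = 3.15 | 0.873 |

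**6. Optional covariate adjustment, n = 28 per arm.** Effective d = 0.8/√(1 − r²), df = 56 − 4 = 52, where r is an assumed correlation between baseline and 24 h BSSI. For r = 0.3, 0.5 and 0.7, effective d is 0.839, 0.924 and 1.120, and power is 0.869, 0.924 and 0.984.

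**7. Conditional risk.** If 4 h or 24 h were chosen after seeing the data, the false-positive rate would be 1 − P(|Z₁| ≤ 1.96 and |Z₂| ≤ 1.96). For assumed correlations of 0.5, 0.7 and 0.9 between the two test statistics this is 0.091, 0.083 and 0.070, against 0.05.

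**The case against.** The best reply is that the plan does fix the decisive time. Section 9.3 sets Hypothesis 1 at 24 h, section 9.2 fixes the scale, and one week is expressly secondary. That stands. A reader might infer that the primary time is open altogether, but the documents do not support this: what is missing is the link from the hypothesis to a test. Step 3 of the Experimental Procedure names 4 h and 24 h together, but it is a procedural sentence and does not displace Hypothesis 1.

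A reader might also infer that 24 h is left out of the analysis. It is not. The repeated-measures rows cover it, and the first can be run as ANOVA at 62. The gap is one of designation.

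Appendix D's data collection sheet, which section 11.1 cites for the variables, is not shown and could define T4. If it does, the label problem shrinks, but there would still be no row named primary and a label that disagrees with Table 2.

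The conflict between 62 and 74 can be softened, because section 11.5 derives its larger samples for models with three to five predictors and the footnoted row is the one with most covariates. That does not settle the MADRS-only row, since the opening sentence of that paragraph is not limited by predictor count.

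Finally, losses may exceed 10%, because section 10.1 drops patients whose infusion is stopped and section 11.1 excludes those with too few BSSI items. At 25 per arm power would be 79%. It is also true that a comparison of mean BSSI does not by itself show that a fall is clinically significant; that question is separate and is not resolved here.

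**Conclusion.** The point holds and must be fixed. The primary hypothesis is at 24 h, and no row of Table 6 is written as its test. On either natural reading of T4, the dated between-arm SI comparison is at another visit. This rests on the text available, with Appendix D unseen; that no row is named primary does not depend on the meaning of T4.

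The documents do not support a claim that the trial is underpowered for its primary question. On the plan's d = 0.8, if it applies at 24 h, 62 subjects suffice: 84% power with 28 per arm. Nor do they give a one-week effect from which a loss of power under a one-week reading could be computed. The false-positive rate of about 7% to 9% is only the risk if the time were chosen after seeing the data despite Hypothesis 1, and it depends on an assumed correlation of 0.9 to 0.5. It is not a property of the plan as written.

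**What to change.** 1. In the SI t-test row of Table 6, replace T4 with t2 (24 to 36 h window, section 10.1) and name that ketamine-versus-saline comparison of BSSI the single primary analysis at two-sided 0.05.
2. Replace the other T4 entries with Table 2 labels.
3. Word Hypothesis 1 as ketamine versus saline at 24 h.
4. In step 3 of the Experimental Procedure, state that 24 h is primary and 4 h secondary. Keep one week and MADRS-S secondary.
5. Reconcile section 11.5 with the Table 6 footnote by stating the sample size at which the mixed model is used and what replaces it below that size, including for the MADRS-only row.
6. Optional, at no cost: run the primary comparison as an ANCOVA with baseline BSSI and the mood-disorder stratum. Both are already collected, and section 11.1 already intends to use the stratification factor as a covariate in multivariate models.

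The cost is wording in sections 9.3, 10.1, 11.5 and 11.6. There are no new visits, data or patients. It should be done before anyone sees outcome data by arm.

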## Randomization Procedures

Randomization will be done through permuted block randomization and stratified for history of mood disorder (e.g., major depression, bipolar disorder, dysthymia). Due to the small size of this study, block randomization will ensure an equal number of treatment and controls. Randomization can lead to unbalanced groups with respect to prognostic factor. Because 60% of those who commit suicide have a mood disorder, this study will be stratified by this prognostic factor. This computer-generated list, will provide a subject identifier. This list of subject identifier and procedure status will serve secondarily as an audit trail

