**10.14 Managing Data (Data Management and/or Sharing Plan) and/or Human Biological Specimens for this Study:**

Include in this section the plan for acquiring data (both electronic and hard copy), access during the study, data/specimen storage and length of time stored, shipment/transmission, and the plan for storage and final disposition at the conclusion of the study. Describe any data agreements in place for accessing data within and/or outside of your institution (e.g., Data Sharing Agreement, Data Use Agreement, Business Agreements, etc.)

Protection and Security of Data and Identifying Information

1. Handling of paper questionnaires will be as follows:
  1. Questionnaires will be placed in trial mailbox.
  2. They will be kept in a locked box in a locked office, until they can be scanned into a secure digital folder.
2. Digital protection:
  1. Data will be stored in accordance to Navy HRPO policy and data storage policies
  2. Password protection: Each patient will be assigned a subject identifier during randomization. This file will be password protected.
    1. The data will remain on a study team member's computer which is only accessible with a CAC card.
  3. De-Identification: Only subject identifiers will be used in psychometric testing. Additionally, as shown in Figure 2, the subject identifier will be the only means to connect to various data related to the subject. The Subject identifier will be stored separate from all de-identified information.
  4. Separation of data: Data collection sheets will be separated into different files, as shown in Table 3.

**Figure 2:** Subject Identifier connection to other data sheets for a participant

**Table 3:** Security Management breakdown of Data Collection Sheets

| Spreadsheet            | Contents  | Who has access?     | Security           |
|------------------------|---|---------------------|--------------------|
| Subject Identifier key | Subject identifier code & Patient name  | NMCCL Investigators | Password protected |
| Demographics           | Email, gender, DOB, age, number of previous attempted suicide, history of self-harm, psychiatric history, | Only Investigators  | Separate file      |

|       |  |                    |               |
|-------|--|--------------------|---------------|
|       | recent antidepressant use, current psychotropic medication, classification (military/civilian) |                    |               |

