**STATISTICAL ANALYSIS**

All data analysis will be carried out using SPSS ® Version 25. Tableau Desktop 2018.1 will be used to augment the creation of graphs. See 3.7.C for power calculation and sample size derivation. If subjects do not complete a baseline, they will not be incorporated in the analysis. A recent clinical study validated that an average of four items from the SSI, with a cut-off of  $\geq 2$ , is sufficient in classifying patients as high risk vs. low risk. Therefore, any patient who does not complete at least four items on the SSI during each of the post administration time points will be excluded from the study. Missing data will be excluded from analysis as long as the degree of freedom permits. The type of data analysis will be in accordance to the Test plan, Table 6. Each arm of the trial will be considered a "group." Appendix D: Sample Data Collection Sheet describes demographic data points as well as measurement scale of each of the below variables. Stratification factors will be accounted for as a covariate in multivariate models.

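### The two t-test rows in Table 6 leave out the same-scale baseline score and the randomisation stratum; ANCOVA would usually be more precise at almost no cost

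*Combined protocol and SAP*

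**What the plan says.** In Table 6 (section 11.6), the rows that ask whether suicidal ideation and depression differ between ketamine and placebo each use a "2 Independent sample t test". The independent variable is group, and the outcomes are BSSI at T4 and MADRS at T4.

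Information that these rows could use is already collected:

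- **Baseline scores.** Section 10.1 (General Approach) has patients complete BSSI and MADRS-S before dosing: "These measures will serve as baseline severity of suicidal wishes and plans, and degree of depression symptoms". Section 11.1 makes the baseline a condition of analysis: "If subjects do not complete a baseline, they will not be incorporated in the analysis".
- **Stratum.** Under Randomization Procedures, history of mood disorder is treated as prognostic, and "this study will be stratified by this prognostic factor".

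Some adjustment is planned elsewhere. Section 11.1 says "Stratification factors will be accounted for as a covariate in multivariate models". The MANCOVA row has "Covariates: Demographics"; the Demographics sheet in Table 3 (section 10.14) includes "number of previous attempted suicide, history of self-harm, psychiatric history", but BSSI and MADRS results are kept on other sheets. The mixed-model rows take BSSI as outcome, two of them with MADRS as a covariate. No row names a baseline score of the outcome scale as a covariate.

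**The concern.** The plan excludes a patient who has no baseline, and then makes no use of the baseline in its two most direct between-arm tests. It also stratifies on a factor it regards as prognostic and tests as though it had not. The section 11.1 sentence on stratification factors concerns multivariate models, so it does not reach a two-sample t-test.

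What is at stake is precision, not bias. If the pre-dose score predicts the post-dose score even modestly, ANCOVA gives a narrower interval from the same patients. This matters more if the true effect is below the planned d = 0.8. Section 11.5 itself notes that this population is broader than in the earlier studies. A smaller issue is that, if the stratum predicts outcome, a t-test that ignores it is somewhat conservative.

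**Working it through.** **1. The plan's own figures (section 11.5).** A two-sided 5% two-sample t-test with 80% power, by noncentral t, needs 25.52 per arm at d = 0.8 and 63.77 at d = 0.5. The plan has 25.5 and 63.7. Its 28.2 for a large correlation reproduces as 28.25 if large means 0.5. Adding 10% to 56 gives 56 × 1.1 = 61.6, hence 62. The sample size reproduces, and the t-test is part of its basis.

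**2. Inputs for the comparison.**
- From the documents: 31 per arm, 10% dropout, two-tailed 5% (the tails are inferred from step 1), d = 0.8 and d = 0.5. Analysed per arm: 31 × 0.9 = 27.9, so N = 55.8.
- Assumed: the baseline-outcome correlation r, at 0, 0.3, 0.5 and 0.7. Section 12.5 enrols only patients with active ideation who are being admitted, which may narrow the baseline range and lower r.

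**3. Formulas.**
- t-test: df = N − 2 = 53.8; noncentrality d / √(2/27.9), which is 2.988 at d = 0.8.
- ANCOVA with two covariates: df = N − 4 = 51.8; variance multiplied by (1 − r²) and by the chance-imbalance factor 1 + q/(N − 3 − q).
- q = 1 (stratum balanced by design, baseline imbalanced by chance): 1 + 1/51.8 = 1.019, so the standard error is 1.0% larger at r = 0.
- q = 2 (both imbalanced by chance): 1 + 2/50.8 = 1.039, so 1.9% larger.

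**4. Results** (each range runs from q = 2 to q = 1 for power, and the reverse for the detectable effect).

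| | t-test | ANCOVA r = 0 | r = 0.3 | r = 0.5 | r = 0.7 |
|---|---|---|---|---|---|
| Power, d = 0.8 | 0.835 | 0.820–0.828 | 0.854–0.861 | 0.913–0.918 | 0.981–0.982 |
| Power, d = 0.5 | 0.450 | 0.436–0.443 | 0.470–0.477 | 0.546–0.554 | 0.711–0.720 |
| Effect detectable with 80% power (SD) | 0.764 | 0.772–0.779 | 0.736–0.743 | 0.668–0.675 | 0.551–0.557 |

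**5. Break-even.** On variance alone, r = √(q/(N − 3)): √(1/52.8) = 0.138 and √(2/52.8) = 0.195. Counting the lost degrees of freedom as well, power is equal at r = 0.143 and r = 0.198, at either effect size. That is about 2% to 4% of outcome variance explained (0.143² = 0.020; 0.198² = 0.039).

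**6. Check by simulation.** With 62 randomised 31:31 in balanced strata (60% assumed to have a mood disorder), 6 lost at random and 60,000 trials per setting, ANCOVA power at d = 0.8 was 0.827, 0.861, 0.918 and 0.981 for r = 0, 0.3, 0.5 and 0.7. These agree with the q = 1 ends of the table.

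**7. Type I error of the unadjusted t-test.** In the same loss model, with r = 0.3 and an assumed 40% to 80% with a mood disorder, it was about 5% with no outcome gap between strata, 4.4% to 4.5% with a gap of 0.5 SD, and 3.1% to 3.8% with a gap of 1.0 SD. A repeat simulation gave 4.2% to 4.7% and 3.0% to 3.6% for the two gaps. ANCOVA stayed at 4.9% to 5.2%.

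**The case against.** The strongest reply is that a valid test, powered above its target at the planned effect, is being exchanged for a usually better one on the strength of a correlation that nobody has supplied. That is fair. Below r of about 0.14 ANCOVA loses slightly, at 0.2 it gains 0 to 0.7 points at d = 0.8, and a gain of about 5 points needs r near 0.4. Correlation may also depend on what T4 is: if it is the one-week contact, a study evaluator gives the BSSI by phone, whereas the baseline is a self-completed paper form.

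The reply also points to what other rows do. On a plain reading, section 11.1 puts the stratum into every multivariate row. The repeated-measures row offers an ANOVA alternative that need not wait for 74 subjects, and section 10.1 counts the pre-dose form among the time points: "Questionnaires will be repeated at four time points for both arms, once in the ED before drug administration". Baseline BSSI may therefore enter there. This narrows the point to the two t-test rows but does not remove it: Table 6 does not say that the pre-dose score is included, and MADRS has no longitudinal row as an outcome.

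Two further points stand. Low power at d = 0.5 is mainly a sample-size matter, since ANCOVA stays below 60% there even at r = 0.5. The type I error shift is on the safe side and rests on assumed stratum shares and gaps. The 0.20 end of the break-even is also pessimistic, because stratified blocks limit imbalance and a prognostic stratum would lower the threshold.

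**Conclusion.** The concern holds, as a recommended improvement confined to the two t-test rows. Those tests are valid and adequately powered for d = 0.8, but they leave collected information unused. The trade is uneven: 0.7 to 1.5 power points lost if neither covariate predicts outcome, against about 2 to 3 points gained at r = 0.3 and about 8 to 10 at r = 0.5. It rests on 27.9 analysed per arm and on an r that the documents do not give. Confidence is medium, because whether r passes 0.14 to 0.20 here is a judgement, though a low bar for the same patient on the same scale.

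**What to change.** First define T4. Table 2 (section 10.1) labels its visits t0 to t3 only, and Hypothesis 1 (section 9.3) concerns 24 hours; the label and the hypothesis need to be reconciled. Then replace the two t-test rows with ANCOVA of the post-dose score on arm, the baseline score of the same scale, and history of mood disorder as used in randomisation. Keep the t-test as a supportive analysis.

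ANCOVA at one time point does not depend on the 74-subject condition that section 11.5 sets for the linear model of repeated measures. The change needs SAP wording only, because both covariates are already collected before dosing. The price, if neither predicts outcome, is a standard error 1.0% to 1.9% larger, for example power of 0.436 to 0.443 instead of 0.450 at d = 0.5.
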